8. STUDY INTERVENTION

(SPIRIT #11)

8.1 Identity of Investigationa l Products (treatment / medical device)

(ICH/E6 6.2.1, 6.4.2, 6.4.4; AGEK Checklist 2, item 3)

ICH: A descripti on of the trial treatment(s) and the dosage and dosage regimen of the investigational produ ct(s).

This section describes all trial treatments for each arm of the study.

8.1.1 Experimental Intervention (treatment / medical device)

ICH: Name and descripti on of the investigational product(s).

All investigational devices are CE marked and based on the Sonova brand hearing system portfolio. This includes hearing systems comprising hearing instruments with hearing instrument software and respective acoustic coupling, fitting software and wireless accessories. The application is done according to the specialised information.

8.1.2 Control Intervention (stan dard/routine/com parator treatment / medical device)

ICH: Name and descripti on of the investigational product(s).

Same as in 8.1.1, whereas the respective sound changing principle is disabled (switched off or switched to a parameter setting with weakest effect) as well as previous hearing instrument technology (containing comparable previous sound changing principles).

8.1.3 Packaging, Labelling and Supply (re-supply)

ICH: Also include a description of the dosage form, packaging, and labelling of the investigational product(s).

N/A

8.1.4 Storage Conditions

All MD and MD supplies have to be stored according to standard procedures as mentioned in the manufacturer directions. The hearing instruments will be stored in their hearing instrument cases (dry and dust-free). There are no special environmental conditions necessary for storage.

8.2 Admini stration of experimental and control interventions

(ICH/E6 6.4.4)

8.2.1 Experimen tal Intervention

ICH: Descripti on of and justification of the treatment(s) to be administered, including the name(s) of all the product(s), the dose(s), the dosing schedule(s), the route/mode(s) of administration, and the treatment period(s), including the follow-up period(s) for subjects for each investigational product treatment/trial treatment group/arm of the trial.

The study is an clinical trial with medical devices.

All medical devices in this trial are CE marked and the application is done according to the specialized information.

Description of route, dose and the rationale for timing of the investigational medical devices, see the following chapters:

- 3.5 Dose Rationale / Medical Device: Rationale for the intended purpose in study (pre-market MD)
- 6.1 General study design and justification of design

Description of study procedures, use and estimated exposure to humans, see the following chapters:

- STUDY SCHEDULE
- 5 STUDY OUTCOMES
- 6.1 General study design and justification of design

8.2.2 Control Intervention

ICH: Description of and justification of the treatment(s) to be administered, including the name(s) of all the product(s), the dose(s), the dosing schedule(s), the route /mode(s) of administration, and the treatment period(s), including the follow-up period(s) for subjects for each investigational product treatment/trial treatment group/arm of the trial.

Same as in 8.2.1

8.3 Dose / Device modifications

(SPIRIT #11b)

N/A

8.4 Compliance with study intervention

(ICH/E6 6.6.3; AGEK Checklist 2, item 2; SPIRIT #11c)
ICH: Procedures for monitoring subject compliance.

N/A

8.5 Data Collection and Follow-up for withdrawn participants

(ICH/E6 6.5.3; AGEK 9.2; SPIRIT #18b)

ICH:b) The type and timing of the data to be collected for withdrawn subjects. d) The follow-up for subjects withdrawn from investigational product treatment/trial treatment.

The subjects participate on a voluntary basis and can abort the participation on the study at any point of the study. The withdrawn subject will be replaced by another voluntary subject. The measurement results of the withdrawn subject will be included to the evaluation if data are complete for the appropriate trial. The new subject has to pass each study trial from the beginning.

8.6 Trial specific preventive measures

(ICH/E6 6.6.2; AGEK 9; SPIRIT #11d)

ICH: Medication(s)/treatment(s) permitted (including rescue medication) and not permitted before and/or during the trial.

To avoid discomfort through too loud output levels of the hearing instruments which could harm the subjects ear, the uncomfortable level (UCL) will be measured within the pure tone audiogram during the screening appointment. The UCL will be used for the fitting of the hearing instruments to ensure a comfortable maximum power output.

After fitting the hearing instruments to the individual hearing loss of the subject, the subjective acceptance of loud input signals will be tested (tolerance test) to ensure that the individual maximum power output (based on the UCL measurement) of the hearing instruments is guaranteed and accepted by the subject.

8.7 Concomitant Interventions (treatments)

(ICH/E6 6.6.2; AGEK 9; SPIRIT #11d)

ICH: Medication(s)/treatment(s) permitted (including rescue medication) and not permitted before and/or during the trial.

N/A

8.8 Study Drug / Medical Device Accountability

(ICH/E6 6.4.7; AGEK Checklist 2, item 1; SPIRIT 11c)

ICH: Accountability procedures for the investigational product(s), including the placebo(s) and comparator(s), if any.

N/A

8.9 Return or Disposition of Study Drug / Medical Device

(AGEK Checklist 2, item 1; SPIRIT 11c)

At the end of the study during the final appointment, all study devices will be returned to the according PI.

9. STUDY ASSESSMENTS

(ICH/E6 6.7, 6.8; AGEK 6, 7; SPIRIT #18a)

This section includes a description of the procedures, measurements, collections and storage of samples taken.

9.1 Study flow chart(s) / table of study procedures and assessments

Each study is a combination of a pre-study and a main study. Each study part consists of a screening, study appointments and one follow-up appointment.

Several pre-studies may be necessary and conducted. The Schedule for a pre-study is visualized in Table 7Table 1. The number of the pre-study appointments may vary whereas a minimum of 3 appointments and a maximum of 6 appointments is considered. The main study represents the actual study for the investigation of one sound changing principle. The results from the pre studies are used to specify the main study. The Schedule is visualized in Table 8. The number of the study appointments may vary depending on the number of tests and test methods being executed for a respective sound changing principle. For a main study a minimum of 4 and a maximum of 8 study appointments is considered. Please note the following tables repeat those of the section STUDY SCHEDULE.

Table 7: Pre-Study schedule

Study Period	Screening	Pre-study appointments				Follow-up (final appointment)
Visit Number	1	2	(3)	(4)	(5)	3...6
Time [hrs]	1.5	2	(2)	(2)	(2)	2
Subject Information and Informed Consent	x					
Audiological History	x					
Physical Examination of Ear and Ear Canal	x	x	(x)	(x)	(x)	x
Audiogram	x					x
Check In- /Exclusion Criteria	x					
Decision Subject Participation	x					
Encoded Subject ID	x					
Fitting HI		x	(x)	(x)	(x)	(x)
Objective Measurements		x	(x)	(x)	(x)	(x)
Subjective Measurements		x	(x)	(x)	(x)	(x)
Introduction to Handling (depending on randomisation list for home trials)		x	(x)	(x)	(x)	
Scheduling Next Visit	x	x	(x)	(x)	(x)	
Capture of Adverse Events and Device Deficiencies		x	(x)	(x)	(x)	x

Table 8: Main study schedule

Study Period	Screening	Main study appointments							Follow-up (final appointment)
Visit Number	1	2	3	(4)	(5)	(6)	(7)	4...8	
Time [hrs]	1.5	2	2	(2)	(2)	(2)	(2)	2	
Subject Information and Informed Consent	x								
Audiological History	x								
Physical Examination of Ear and Ear Canal	x	x	x	(x)	(x)	(x)	(x)	x	
Audiogram	x								x
Check In- /Exclusion Criteria	x								
Decision Subject Participation	x								
Encoded Subject ID	x								
Fitting HI		x	x	(x)	(x)	(x)	(x)	(x)	
Objective Measurements		x	x	(x)	(x)	(x)	(x)	(x)	
Subjective Measurements		x	x	(x)	(x)	(x)	(x)	(x)	
Introduction to Handling (depending on randomisation list for home trials)		x	x	(x)	(x)	(x)	(x)		
Scheduling Next Visit	x	x	x	(x)	(x)	(x)	(x)		
Capture of Adverse Events and Device Deficiencies	x	x	x	(x)	(x)	(x)	(x)	x	

9.2 Assessments of out comes

ICH: Specification of the efficacy parameters. Specification of safety parameters.

This section includes a description of each endpoint, what variables will be assessed/observed and how it will be done, including any related processes to promote data quality.

9.2.1 Assessment of primary outcome

ICH: Methods and timing for assessing, recording, and analysing of efficacy & safety parameters.

The primary outcomes are the laboratory test results (Reference to section 5.1 Primary Outcome). These tests intend to determine the hearing performance provided by the device. They are conducted with help of corresponding measurement tools, whereas the results are stored automatically in an appropriate format (e.g. xls file). Depending on the investigated sound changing principle the suited outcome measurement is chosen. The respective measurements are carried out at each study appointment. In general the content of these assessments in one sub-study includes measurements to investigate one of the three hearing performance dimensions (speech intelligibility, signal clarity, sound quality / hearing comfort). The respective other hearing dimensions may be investigated additionally to examine trade-off aspects. As well the investigational application and the comparator have to pass the same measurements to get comparable data. With help of the received data it can be concluded whether the experimental condition is superior to the comparator with regard to hearing performance.

9.2.2 Assessment of secondary outcomes

ICH: Methods and timing for assessing, recording, and analysing of efficacy & safety parameters.

The secondary outcomes are the subjective test results of questionnaires during tests in real world environment (Reference to section 5.2 Secondary Outcomes). This includes home trials and may include guided walks. This assessment will be done between the appointments (home trials) and/or at specifically defined study appointments (guided walks). Depending on the investigated sound changing principle the suited outcome measurement is chosen. With the questionnaire as well the investigational application and the comparator are subjectively evaluated by the participants. Depending on the study part, the questionnaire will be filled out directly in the laboratory or in an home trial.

9.2.3 Assessment of other outcomes of interest

ICH: Methods and timing for assessing, recording, and analysing of efficacy & safety parameters.

Other outcomes of interest like side-effects will be carefully investigated, evaluated and documented. This outcome will also be documented in the form of questionnaires. Additional further measurements (investigating basic psychoacoustic function for instance) will be done at specifically defined study appointments if necessary (Reference to section 5.3 Other Outcomes of Interest).

9.2.4 Assessment of safety outcomes

ICH E6 6.8: Specification of safety parameters. The methods and timing for assessing, recording, and analysing safety parameters

9.2.4.1 Adverse events

Basically, all participants will be instructed to immediately report any problems, oddness or difficulties which occurred with or through the testing devices by contacting the appropriate investigator. Additionally, the investigator will request the same after each home trial at the beginning of the subject appointment. Any feedback will be recorded in the appropriate eCRF.

9.2.4.2 Laboratory parameters

N/A

9.2.4.3 Vital signs

N/A

9.2.5 Assessments in participants who prematurely stop the study

Withdraw without Adverse Event: If a subject is withdrawn from the study without having an Adverse Event (AE), an audiogram will be recorded in a final appointment and the outer ear will be controlled to ensure that there are no damages through the study.

Withdraw with Adverse Event: If a subject is withdrawn in case of an AE, a referral to an independent doctor will be carried out. In accordance with the subject and the doctor, an additional appointment will be arranged to record a status update.

9.3 Procedures at each visit

Each study part follows the same pattern:

- Pre-Study
 - Screening
 - Pre-study appointments
 - Follow Up
- Main study

- Screening
- Main study appointments
- Follow Up

This pattern ensures the best method to not unnecessarily extend the study and to not perform tests with subjects, which are not needed. For that reason first a pre-study is conducted with only a few participants to test and determine sensitive outcome measures and promising parameter adjustments of the sound changing principle. The aim of the pre-study is to proof the study concept and the scientific interrogation behind it. Several pre-studies may be carried out. If the results of the pre-study are promising, the main study will start.

9.3.1 Screening Appointment

- Mapping to an encoded and randomized subject ID
- Discussion of the subject information and signing of the informed consent which were sent in advance by post or email
- Recording of the subject's audiological history
- Ear and ear canal assessment (otoscopy)
- Hearing test (pure tone and speech audiometry)
- In case of tinnitus: Tinnitus Pitch and Loudness Matching
- Explanation of in-/exclusion criteria
- Decision if patient can participate in the trial regarding to the in-/exclusion criteria
- Scheduling of the next visit

9.3.2 Pre-study appointment

- Ear canal assessment
- Fitting of hearing instrument (randomized)
- Measurements objective and subjective (randomized), see section 9.2.1 and 9.2.2
- Fine tuning hearing instrument, if necessary
- Introduction to handling of hearing system (randomized)
- Signing of the device delivery form
- Schedule next visit

9.3.3 Main study appointments

A main study appointment will only be executed if the pre-study results were promising. The procedure for the main study appointments is the same as for the pre-study appointments (see section 9.3.2).

9.3.4 Final appointment

- Ear canal assessment
- Measurements objective and subjective (randomized), see section 9.2.1 and 9.2.2
- Hearing test (pure tone)
- Calculation and signing of the compensation form
- Signing of the device return form
- Collecting all study material
- Hand out of study feedback form

10. SAFETY

(Clin O Art. 37-43; ICH/E6 6.8; ISO14155 8.2.5, A.14; AGEK 4.1; SPIRIT # 22, 30)

Description of plans for collecting, documenting, assessing, reporting, and managing solicited and spontaneously reported adverse events and other unintended effects of trial interventions or trial conduct.

10.1 Drug studies

N/A

10.2 Medical Device Category C studies

N/A

10.3 Medical Device Category A studies

10.3.1 Definition and Assessment of safety related events

All hearing systems are CE-labelled, i.e. the safety of the user is granted. However, the hearing instrument can reach a high maximum power output (MPO) which can be louder than the user's threshold of uncomfortable levels is. For this reason, the MPO will always be set accordingly to clinical expertise at a level so that no injuries can occur (Refer to 8.6 Trial specific preventive measures). Consequently, neither during the measurements nor in the daily routine the safety of the participants will be compromised.

In order to ensure that each MD works correctly, every device will be checked before each application by the appropriate investigator. Furthermore, the participant is instructed to take note of any unexpected incidences (e.g. redness or swelling of the outer ear) and to document these in the questionnaires. Pressure points are also controlled by the investigator at the beginning and at the end of an appointment. In the case that wearing the test devices in the time between the appointments becomes uncomfortable or even painful, the subjects are instructed not to wear the devices anymore and to contact the investigator for information and, if necessary, a doctor.

Furthermore, the participants are advised not to wear the device if a setting is not acceptable or tolerable, but to contact the investigator for an additional appointment. If any unexpected incidences occur during the lab trials the participant will be encouraged to immediately report the issue to the investigator.

In all cases of undesirable events the responsible supervising investigator within Sonova must be informed immediately. Where appropriate the test subject will be forwarded to an independent fiduciary doctor for further clarification.

10.3.2 Reporting of Safety related events

Reporting to Sponsor:

Health hazards that require measures are reported to the Sponsor within 24 hours upon becoming aware of the event. If any unexpected AEs are to occur (e.g. chronic pain in the ear canal after MD application), the event has to be documented in the AE eCRF. Depending on the event, a decision needs to be made whether the participation in the study has to be interrupted or even cancelled. If required, a referral to an independent doctor is to be carried out. An additional appointment will be arranged with the test participant (e.g. after one to two weeks) in order to record and document the status update.

Reporting to authorities:

In Category A studies it is the investigator's responsibility to report health hazards requiring measures to the local Ethics Committee within 2 days.

11. STATISTICAL METHODS

(ICH/E6 6.9; AGEK 8; SPIRIT # 14, 20)

Statistical considerations

ICH: A description of the statistical methods to be employed, including timing of any planned interim analysis(ses).

This section describes the statistical considerations done for the study and the level of significance that will be used. The traceability of the study data is warranted for both the pre-study and the main study at any time.

11.1 Hypothesis

This is a methodical evaluation in which different parameter settings of novel sound changing principles in hearing instruments shall be investigated and new hardware and software technologies of Sonova brand products shall be compared with previous outstanding Sonova brand hearing systems. Hence, this study will not test a specific hypothesis.

11.2 Determination of Sample Size

ICH: The number of subjects planned to be enrolled. In multicentre trials, the numbers of enrolled subjects projected for each trial site should be specified. Reason for choice of sample size, including reflections on (or calculations of) the power of the trial and clinical justification.

Based on numerous publications in the field of audiology research using standardized measurement methods testing hearing impaired subjects as well as on Sonova AG's extensive study experience, a number of maximum 20 - 25 subjects per study is sufficient to obtain statistically significant results on a significance level of 5%.

In the case of the pre-study a maximum of 5 subjects is included, since merely the study concept needs to be proven, and no inferential but only descriptive statistics is carried out. Later, during the main study, both descriptive and inferential statistics are executed. In the past, typically 20 subjects participated per study leading to significant results approaching the primary objective (determine and assess the performance of novel sound changing principles in hearing instruments). To tackle the secondary objective (investigate and assess the effect of the respective sound changing principles in real world environment) mainly descriptive statistics is carried out.

11.3 Statistical criteria of termination of trial

ICH: A description of the "stopping rules" or "discontinuation criteria" for individual participants, parts of trial and entire trial.

After each pre-study an analysis is performed. The corresponding results are the basis for the further progress of either an additional pre-study or the main study which might be adjusted accordingly, if necessary. If the study design has to be adjusted severely or changed based on former results this will be reported to the ethics commission via an amendment.

11.4 Planned Analyses

ICH: A description of the statistical methods to be employed, including timing of any planned interim analysis(ses).

In a first step, the distribution of the collected subjective and objective data is verified. Based on this outcome (normally distributed yes/no) and depending on the scale level (nominal, ordinal, interval or rational) of the variables, descriptive statistics is executed in the form of determining the mean value and standard deviation or the median and quartile, respectively. Furthermore, diagrams for visualization are compiled such as boxplots, histograms and scatterplots.

Then, after a determination of the measurement variables regarding their relationship or their difference, inference statistics is executed by applying the appropriate parametric or non-parametric test depending on the data's distribution either using the correlation coefficient (Pearson, Spearman), t-Test, ANOVA, MANOVA, Mann-Whitney-U-Test, or the Wilcoxon-Test. Generally, a significance level of 5% is pursued.

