5.1 Primary Outcome

The primary outcomes are the laboratory test results. These tests intend to evaluate the hearing performance in terms of speech intelligibility, signal clarity and sound quality / hearing comfort. With help of the received data from these outcome measurements it can be concluded whether the experimental condition is superior to the comparator with regard to hearing performance.

Each sub-study focuses specifically on one of these hearing dimensions. The corresponding other hearing dimensions may be additionally examined to investigate a trade-off (e.g. trade-off for speech intelligibility versus sound quality / hearing comfort). Depending on the investigational sound changing principle and the corresponding focused feature or function (aim) the appropriate audiological testing method will be chosen (Table 4).

Table 4: Audiological testing methods for outcome measures in the laboratory

Performance	Aim	Method	Result [unit]
Speech intelligibility	Assessment of speech intelligibility in quiet	Freiburger Sprachtest [13]	Discrimination [%]
	Assessment of speech intelligibility in noise	Oldenburger Satztest (OLSA) [14, 15]	Speech intelligibility threshold in noise [dB SNR]
	Assessment of speech intelligibility in quiet or in noise	Einsilber-Reimtest nach von Wallenberg und Kollmeier (WaKo) (quiet/noise) [16]	Discrimination [%]
	Assessment of speech intelligibility in quiet or in noise	Göttinger Satztest (GöSa) (quiet/noise) [17]	SRT in quiet [dB], in noise [dB SNR]
	Assessment of speech intelligibility with variable target location and talker identity	Coordinate Response Measure [18, 19, 20]	SRT [dB] or performance level (%-correct responses)
	Assessment of cognitive influences on speech perception	Cognitive Measures, e.g. for Working-Memory Capacity (e.g., Reading Span [21]), Executive Functioning and Attention (e.g., Stroop Task), Overall Cognitive Ability (e.g., MoCA [22])	Performance Level [%-correct responses or time-to-complete outcomes]
	Objective Assessment of Listening Effort and Spare Capacity	Response Delays during above listed Speech Intelligibility Tests; Dual-Task Paradigms with Speech Intelligibility as primary task and a Cognitive Outcome Measure as the Secondary Add-On Task (e.g., Assessment of Cognitive Capacity for tasks of Selective Attention or Working Memory during the Primary Task [23, 24, 25])	SRT [%] and Errors [%] or Response Times [ms]

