11.4.1 Datasets to be analysed, analysis populations

ICH: The selection of subjects to be included in the analyses (e.g., all randomized subjects, all dosed subjects, all eligible subjects, evaluable subjects).

The data of all participants and measurement methods will be analysed. Subgroups typically composed are hearing loss dependent groups (mild, moderate, severe, profound) and groups depending on their experience level wearing hearing instruments or using accessories (non-experienced, short-term, experienced, long-term user). In case of a subject withdrawal, the statistician will decide if the data can be used for a part of the statistical analysis or if the data will be dropped out completely.

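### Superiority is to be concluded from tests at a general 5% level, but no sub-study has to record its outcome, contrast, sidedness or multiplicity rule before main-study data are seen

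*Combined protocol and SAP*

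**What the plan says.** The statement on hypotheses in section 11.1 is "Hence, this study will not test a specific hypothesis".

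The outcome sections go further. Section 5.1 defines the endpoint in the plural, "The primary outcomes are the laboratory test results", and says that from these data "it can be concluded whether the experimental condition is superior to the comparator with regard to hearing performance". Section 9.2.1 repeats this: "With help of the received data it can be concluded whether the experimental condition is superior to the comparator".

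The statistical sections then plan tests. Section 11.2 states "Later, during the main study, both descriptive and inferential statistics are executed" and justifies 20 to 25 subjects by significance at 5%. Section 11.4 lists correlation coefficients, t-test, ANOVA, MANOVA, Mann-Whitney and Wilcoxon tests and closes with "Generally, a significance level of 5% is pursued". Section 11.4.1 adds "The data of all participants and measurement methods will be analysed". Section 11.4.3 handles secondary analyses like the primary one.

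Some text narrows the choices. Section 5.1 gives each sub-study one focused hearing dimension and treats the rest as optional: "The corresponding other hearing dimensions may be additionally examined to investigate a trade-off". The synopsis and sections 4.2, 5.1 and 9.2.1 speak of one suited measure or method. The Study Schedule and sections 9.1 and 9.3 use the pre-study to find sensitive measures and promising settings and to specify the main study.

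Other text keeps several tests open: the number of comparators may vary (3.6), several parameter settings are examined (4.2), and a sub-study may use several test methods (6.2.1).

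**The concern.** A conclusion of superiority at a 5% level is a hypothesis test, whatever section 11.1 calls it. Its error rate is known only if it is clear beforehand which outcome and contrast carry the conclusion, whether 5% is one- or two-sided, and what happens when several tests are run. The plan states neither sidedness nor a multiplicity rule, and it sets no point at which a sub-study must record its outcome and contrast.

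With several settings or methods, a novel setting could be called superior because one of several unadjusted tests crossed 5%. The reader of a sub-study report could not tell this from a single planned test that succeeded. The stated purpose of the results is to steer hearing instrument development and the choice of settings, so a false superiority finding has a practical consequence.

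**Working it through.** **1. The plan's own figure.** The only statistical figure is 20–25 subjects (11.2). It cannot be reproduced, because effect size, standard deviation, power and sidedness are not given. Working backwards for a paired t-test at 5% and 80% power, 20 subjects detect a standardised paired difference of 0.66 (two-sided) or 0.58 (one-sided). For 25 subjects the figures are 0.58 and 0.51. Unstated sidedness alone changes what the sample size can show.

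**2. Is there a rule elsewhere?** The nearest candidates are:
- Study Schedule, 9.1, 9.3: the pre-study informs the main study. Nothing says what must be recorded, where, or by when.
- 6.1: a power analysis would force a named outcome and contrast, but it is done only where possible.
- 11.3: an amendment is needed only for a severe adjustment or change of design.
- 11.4.6: deviations are reported, but the plan they would deviate from fixes none of the four items.
- 12.3: monitoring takes account of sub-study endpoints, without requiring them to be written down in advance.

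**3. False superiority if tests are unadjusted.** Inputs from the documents: cross-over (paired data), n = 20, 5% level. Assumptions: two-sided tests, one comparator, no true difference, a paired t-test for every novel setting and outcome, and outcome correlation 0.5. Outcomes here are methods within the focused dimension, not trade-off measures.

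For one test, false superiority is 0.05/2 = 2.5%. For k independent tests it is 1 − (1 − 0.025)^k: 4.9% for k = 2, 7.3% for k = 3, 14.1% for k = 6, 20.4% for k = 9. Contrasts share a comparator and outcomes are correlated, so simulation (100,000 replicates) gives lower values:

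| Novel settings | Outcomes | Tests | False superiority | Correlation 0.8 to 0 |
|---|---|---|---|---|
| 1 | 1 | 1 | 2.5% | – |
| 2 | 1 | 2 | 4.6% | – |
| 1 | 3 | 3 | 6.3% | 5–7% |
| 2 | 3 | 6 | 11% | 9–13% |
| 3 | 3 | 9 | 15% | 12–18% |

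At n = 25 the results are nearly the same (4.6%, 6.4%, 11%, 15% for the last four rows). If 5% is meant one-sided, the first row is 5%.

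**4. If ANOVA were a required first step for each outcome.** The rates become 2.0% (two novel settings, one outcome), 5.4% (two, three) and 5.2% (three, three). With one novel setting there are only two conditions, the ANOVA equals the paired t-test, and 6.3% is unchanged.

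**5. If one primary contrast is tested first and the rest by Holm only after it succeeds.** False superiority is 2.4–2.6% in all five rows. If the primary contrast is truly superior by 0.66 SD and the others are null, false superiority of another contrast is 2.1–2.5%. Unadjusted, it is 9.9% and 14% in the last two rows.

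**The case against.** Four points deserve weight.

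First, several sections describe the choice of measure in the singular, and section 6.2.1 does not say that several test methods belong to the same dimension; they may be trade-off measures. No section shows three outcomes in one dimension. This stands: the one-outcome rows (2.5% and 4.6%) follow most directly from the text, and the three-outcome rows are conditional.

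Second, the pre-study is meant to find the most promising setting, which makes many settings in the main study less typical. This also stands, but sections 3.6 and 4.2 still allow several.

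Third, section 11.4 calls for an appropriate test and lists ANOVA and MANOVA, which address several settings and outcomes. That is fair against reading 11% and 15% as expected rates. It does not close the gap, because both are options in a list and not required first steps. No figure for a MANOVA gate was calculated.

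Fourth, the protocol describes a series of studies, so section 11.1 may mean only that the umbrella has no single hypothesis. That softens the conflict, but it leaves the superiority wording in 5.1 and 9.2.1 without a rule.

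A reader might infer that superiority claims from these sub-studies generally carry an 11–15% error rate, or that all 20 method rows of Table 4 are tested together. The documents support neither: they fix no number of tests and give each sub-study one focus. Nor do they show that sub-studies lack their own plans; they show only that none is required to fix these items.

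**Conclusion.** The concern holds as a gap in the rules for sub-studies and should be fixed. Sections 5.1 and 9.2.1 promise a superiority conclusion, sections 11.2 and 11.4 supply tests at a general 5% level, and nothing obliges a sub-study to commit to outcome, contrast, sidedness or multiplicity rule in advance.

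The size depends on a number of tests that the plan does not give. There is no inflation with one contrast and one outcome. The rate roughly doubles, to 4.6%, with two novel settings and one outcome. It reaches 6%, 11% or 15% only if three outcomes in the focused dimension are tested without adjustment. The last two are upper scenarios that an ANOVA gate per outcome would bring down to about 5%. The absence of a rule is certain from the text; how often the larger rates would arise is not.

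**What to change.** Replace the last sentence of 11.1 by: 'After the pre-study and before the first main-study participant, each sub-study records either (a) one primary outcome from its focused dimension and one primary contrast (selected setting versus named comparator), tested once, two-sided at 5%, with any further superiority claim controlled by a familywise procedure recorded in advance (for example Holm); or (b) that it is exploratory, in which case results are reported as estimates with 95% CI and no superiority conclusion is drawn.' Route (b) keeps the present intent of 11.1.

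Under (a), the recorded procedure should say how the primary contrast belongs to the family, for example by testing the rest only if it is significant. Otherwise 5% is spent twice.

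Three sections must follow:
- 11.4: replace "Generally, a significance level of 5% is pursued" by a reference to this rule.
- 11.4.3: secondary analyses are estimates with 95% CI unless included in the recorded procedure.
- 5.1 and 9.2.1: limit the superiority wording to the recorded contrast or contrasts.

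The cost is a few sentences, a short record per sub-study and fewer results that can be called significant. At n = 20 and a paired effect of 0.66 SD, power for the primary contrast is 80% (noncentral t, noncentrality 0.66 × √20 = 2.95). For a further contrast at the first Holm step, alpha is 0.05/2, 0.05/5 or 0.05/8 with 2, 5 or 8 further tests, and power is 70%, 55% or 47%. These counts are the three-outcome rows of the table less the primary test (3 − 1, 6 − 1, 9 − 1). Gating on the primary contrast lowers them further, to about 43% jointly with 8 further tests. Several settings can still be explored and reported as estimates.
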